## 12.1 Power Analyses

Power calculations to estimate the sample sizes required to detect a difference between the rate of change in two groups were based on the two-sample t-test using the formula in Statistical Methods in Medical Research (Armitage and Berry 1994). Sample sizes per arm were estimated using ADNI 12-month change scores for the ADAS-Cog12 for the combined MCI and AD population, targeting power=.80, Type 1 error level=0.05, SD=5.72. Table 5 shows the range of estimates needed to detect absolute change score differences between groups ranging from 1.6-2.6 for dropout rates between 0.15-0.25. These estimates were derived with 6 month intervals between testing, and thus more frequent administration of the ADAS-Cog12 in this trial should provide even greater power. Similarly, a 4-month pilot trial (Craft, Baker et al. 2012) dropout rate was <7%, and although a higher dropout rate is expected with a longer, multi-site trial, the excellent safety profile and incentive of the open-label extension at the end of the trial should maximize retention. The addition of a delayed recall score should increase sensitivity for aMCI participants. For MRI endpoints, sample sizes needed to detect a 25% slowing in mean rate of decline in the entorhinal cortex over a 12-month period ranged from 70 for AD to 280 for aMCI (Holland, Brewer et al. 2009). Given that our n=240-300, and the sample will be composed of both aMCI and AD, we should have adequate power.

**Table 5 | Range of estimates needed to detect absolute change score differences between groups ranging from 1.6-2.6 for dropout rates between 0.15-0.25**

	1.6	1.7	1.8	1.9	2.0	2.1	2.2	2.3	2.4	2.5	2.6
Dropout rate .15	431	382	341	306	276	250	228	209	192	177	163
Dropout rate .175	436	387	345	309	279	253	231	211	194	179	165
Dropout rate .20	441	391	349	313	282	256	233	214	196	181	167
Dropout rate .225	446	395	353	317	286	259	236	216	198	183	169
Dropout rate .25	451	400	357	320	289	262	239	218	201	185	171

### 13.0 POTENTIAL RISKS

#### 13.1 Safety of Intranasal Insulin

Safety issues pertaining to INI administration for the treatment of diabetes have been extensively explored for over two decades (Pontiroli, Alberetto et al. 1982). For diabetes treatment, absorption enhancers must be used to increase the transport of insulin across the nasal membrane to the periphery due to the fact that peripheral bioavailability of insulin without absorption enhancers is less than 1% (Illum 2002). A recent safety study of INI administration without absorption enhancers demonstrated no treatment induced changes in blood glucose levels, nasal airway patency, or transnasal pressure gradient (Kupila, Sipila et al. 2003). There are no known serious risks associated with INI without enhancers. A recent industry report raised the issue of rare but significant increases in lung cancer in smokers treated with inhaled insulin; six of 4740 patients taking inhaled insulin developed lung cancer compared with one of 4292 patients who received an active comparator (incidence per 100 patient years exposure, 0.13 vs 0.02). However, the inhaled insulin protocol used for diabetes treatment in this report included absorption enhancers to maximize delivery to lungs, whereas the nose-to-brain delivery device to be used in this study greatly minimizes lung delivery.

Regarding the risk of hypoglycemia, at least five peer reviewed human studies (Kern, Born et al. 1999; Born, Lange et al. 2002; Kupila, Sipila et al. 2003; Benedict, Hallschmid et al. 2004; Stockhorst, de Fries et al. Submitted for publication) and four preliminary studies (Reger, Watson et al. 2006; Reger, Watson et al. 2008; Reger, Watson et al. 2008) (Craft, Baker et al. 2012) revealed no change in blood glucose levels following intranasal insulin administration with doses that included 40 IU 4 times daily for two months. There was one exception with the case of a single participant who experienced mild hypoglycemia (52 mg/dl) after skipping a meal and engaging in sustained vigorous exercise. In addition, a recent safety study (Kupila, Sipila et al. 2003) examined intranasal insulin administration of 60 IU once a day for three weeks in 20 healthy adults. This randomized, double-blind, placebo-controlled crossover trial measured blood glucose levels six times a day during the first two and the last two days of treatment. Pre- and post-treatment blood laboratory tests and nasal examinations were performed. The nasal studies included rhinoscopy to detect local irritation, a saccharin particle test to analyze mucociliary clearance, and rhinomanometry to evaluate nasal airway patency and transnasal pressure gradient. Results indicated no change in blood glucose values with insulin, and no change in the frequency of glucose values above 3.0 mmol/L. The only symptomatic hypoglycemic value occurred during placebo treatment. Insulin treatment had no effect on other laboratory values (C-peptide, total cholesterol, HDL, LDL, triglycerides, creatinine, glutamyl transferase), blood pressure, or body weight. In addition, nasal examinations revealed no adverse effects or functional disturbances following intranasal insulin administration. No serious adverse effects of treatment were observed in the preliminary studies (Reger, Watson et al. 2006; Reger, Watson et al. 2008; Reger, Watson et al. 2008; Craft, Baker et al. 2012). However,

there are fewer safety data for INI use by patients with AD and it is possible that long-term administration may induce CNS hyperinsulinemia or insulin resistance that may have deleterious effects. Such effects would presumably manifest as accelerated cognitive or functional decline. Thus an intensive safety-monitoring plan will be in place for this study that should detect such patterns and a conservative duration of treatment that balances safety and scientific considerations.

### **13.2 Risks associated with use of the POD device**

There are risks that may occur from use of the investigational intranasal drug administration device, although these are not expected to be serious. It is important that participants carefully follow the instructions they are given about how to administer the study drug and how to maintain the intranasal drug administration device and its components. If they don't carefully follow the instructions it is possible that they may not receive the correct dose. They could also experience some discomfort to their eyes or face if they do not hold the device to their nose as directed. In addition, the contents of the POD device's canister are under pressure and should not be punctured or stored near heat or open flame. Finally, the POD tip on POD device is small and could be a choking hazard for children. The participant and their Study Partner will be trained on proper device operation and asked to maintain the device and its components properly.

### **13.3 Optional Lumbar Puncture**

Lumbar puncture may be associated with pain during the performance of the procedure. This is usually temporary and confined to the lower back. Headache may occur in about 5% of elderly people who undergo lumbar puncture. Less commonly, in about 1-4% of participants, a persistent low-pressure headache may develop, probably due to leakage of CSF. Lower rates of post-LP headache have been noted in elderly patients, and when atraumatic (Sprotte) needles are used. If a post-LP headache persists it may need additional treatment, e.g. with fluids and analgesics. Uncommonly a blood patch (injection of some of the participant's blood to patch the CSF leak) may be needed. Potential but rare risks of lumbar puncture include infection, damage to nerves in the back, and bleeding into the CSF space. The risk of these is much less than 1%.

### **13.4 MRI**

The risks of MRI primarily arise from the possible introduction of ferromagnetic objects into a high magnetic field, which can create a dangerous projectile or lead to dysfunction or heating of an implanted medical device. All participants will be rigorously screened by MRI personnel to be certain that they do not have any medical contraindications for MRI, which include metallic foreign bodies in the brain or eye or cardiac pacemaker. This safety screening is part of routine clinical practice at MRI centers and is performed before any participant is permitted to enter the scanning room. There is a slight risk of anxiety due to claustrophobia. Any participant who experiences anxiety when placed into the MR scanner will be removed from the scanner, offered reassurance by the MR tech doing the scan, and offered the option of continuing or terminating the scan. If the participant decides that the anxiety associated with MRI is uncomfortable for them and they wish to terminate the scan, then the examination will be ended at that time. There will be no attempt to coerce participants to complete exams that they are uncomfortable with. Participants uncomfortable with MRI scans should preferably not be included in this study. Use of anxiolytic agents for completion of MRI scans is discouraged, but allowed at the discretion of the site clinician.

### 13.5 Blood Draw

The risks of blood draw include pain from the needle, bruising or infection at the site of venipuncture, or fainting as a response to blood draw. Approximately 150 mls of blood will be drawn for routine and biomarker laboratory assessments over the course of this trial.

### 14.0 PERSONNEL REQUIREMENTS

The following staff-member roles will be required to conduct the protocol at each site. Details will be provided in the procedures manual.

- **Site Protocol Principal Investigator:** The Site Protocol Principal Investigator (PI) is responsible for the overall conduct of the study at the site. The PI will perform or supervise clinical evaluation of all participants and ensure protocol adherence. The PI will supervise project personnel and ensure that clinical raters maintain a high level of skill and accuracy in conducting assessments. The PI may also perform certain ratings him or herself.
- **Study Clinician:** This person will be responsible for conducting and supervising the medical evaluation (nasal examination, physical and neurological examinations), reviewing adverse events, interpreting laboratory results, and supervising clinical care provided to the participant during the protocol. The study clinician will also perform the optional lumbar punctures. The study clinician may perform the CDR-SB. The study clinician may be a physician, or if consistent with local practice and regulations, a nurse practitioner or physician's assistant. The site Principal Investigator may also serve as the study clinician.
- **Study Coordinator:** This person will be responsible for managing the day-to-day conduct of the trial. Duties may include tracking recruitment, ensuring accurate administration of all instruments at the site, maintaining case report forms, processing of laboratory samples, maintaining a log of treatment adherence, serving as liaison with the clinical monitor, coordinating clinic visits, and administering cognitive assessments.
- **Interviewer/Psychometrician:** This person will be responsible for administering the cognitive and functional assessments. The same individual should not administer both the ADAScog and the CDR-SB.
- **CDR Rater:** This person will render the CDR-SB rating based on clinical assessment of participant and study participant. Since the CDR-SB is a secondary outcome measure, it is important for the CDR rater to remain blinded to ADAS-cog data.
- **ADAS-Cog12 Rater:** This person should be blinded to the CDR-SB data.
- **Regulatory Affairs:** This person will be responsible for managing all regulatory related documents for the duration of the trial, including submitting all required regulatory and essential documents to the Coordinating Center Regulatory Affairs.
- **Billing Remittance and Statement:** This person will be responsible for reviewing and verifying payments from the Coordinating Center are in alignment with procedures completed, along with accepting and processing payments from the Coordinating Center.
- **MRI Contact:** This person will be responsible for conducting phantom and human volunteer scans using the appropriate scanning sequence, for site qualification purposes and as needed to assess for drift. As well as conducting participant MRI scans per protocol.

## 15.0 STUDY DRUG

All participants will take two daily doses of INI (20 IU bid for a total of 40 IU daily) or placebo, administered approximately 30-60 minutes after breakfast and dinner. Participants should be instructed to skip the morning dose of study drug on study visit days to avoid the acute effects of insulin.

### 15.1 Humulin® R U-100 Insulin

Humulin® R U-100 (NDC: 0002-8215, Eli Lilly & Company) is a polypeptide hormone structurally identical to human insulin synthesized through rDNA technology in a special non-disease-producing laboratory strain of *Escherichia coli* bacteria. Humulin R U-100 has the empirical formula  $C_{257}H_{383}N_{65}O_{77}S_6$  and a molecular weight of 5808 Da. Humulin R U-100 is a sterile, clear, aqueous, and colorless solution that contains human insulin (rDNA origin) 100 units/mL, glycerin 16 mg/mL and metacresol 2.5 mg/mL, endogenous zinc (approximately 0.015 mg/100 units) and water for injection. The pH is 7.0 to 7.8. Sodium hydroxide and/or hydrochloric acid may be added during manufacture to adjust the pH.

More information about the Humulin® R U-100 insulin, including risks, contraindication and adverse reactions can be found in the the US package insert (USPI).

### 15.2 Placebo (Sterile Diluent)

The matching placebo/sterile diluent (NDC: 0002-0800-01, Eli Lilly & Company) will be comprised of: Glycerin, 16 mg; Metacresol, 1.6 mg; Phenol, 0.65 mg; Sodium Phosphate Dibasic, 3.8 mg dissolved in 1 ml distilled water.

### 15.3 Randomization

We will use a semi-crossover design (Jarjoura 2003). Initially, eligible participants will be randomized on a 1:1 schedule to receive placebo or 20 IU bid of INI using the following randomization strategy: ApoE-e4 carrier status (yes or no), gender, MMSE score (high, low). Study site and age will be weighted in a covariate-adaptive randomization strategy to achieve optimal balance between treatment arms on important factors that may influence treatment outcome. After 12 months of double-blinded treatment with placebo or 20 IU bid of insulin, all participants will receive 20 IU INI bid in a 6-month, open-label extension.

### 15.4 Blinding

For the initial 12-month period, neither participants, study partners, site personnel, most Coordinating Center staff, nor PI will know whether the participant is receiving active study drug or placebo. Exceptions may be personnel involved in preparing the DSMB reports, members of the DSMB and personnel involved in managing certain aspects of the study drug supply chain.

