### **7.7 Month 12 (Visit 6)**

The Month 12 visit is scheduled 12 months (+/- 2 weeks) from day one of the Baseline visit. Month 12 visit is the last visit before the 6-month open-label period and the visit may occur over multiple days. The MRI should be conducted prior to the LP.

Blood for plasma biomarkers will be collected immediately before participants undergo the optional lumbar puncture. Plasma insulin, glucose, A $\beta$ 40 and A $\beta$ 42 should be measured in the morning after an overnight fast, if possible. Additional plasma, along with serum and peripheral blood mononuclear cells (PBMCs) will be collected and banked. Clinical laboratory evaluations will be conducted to monitor safety and tolerability.

The optional lumbar puncture should be performed in the morning after an overnight fast, if possible. Additionally, CSF sample will be banked for future exploratory analysis. CSF will be collected and immediately frozen upright on dry ice for at least 20 minutes before being packaged along with the frozen plasma to be shipped overnight frozen on dry ice to the central biomarker laboratory. Site staff will call the participant within approximately 24 hours from the LP procedure to inquire about the participant's well being and possible adverse events.

Cognitive and behavioral assessments will be performed. The study procedures will be standardized such that the ADAS-Cog12 will be the first cognitive test administered. Additional assessments include the MMSE, a memory composite (Story Recall and FCSRT), Trail-making Test A and B, the CDR-SB, the ADCS-ADL-MCI and the NPI. The Treatment Blinding Questionnaire and the Research Satisfaction Survey will also be administered. Cognitive and behavioral assessments should not be administered while participants are fasting or immediately after the LP procedure.

In addition, vital signs and weight will be obtained, physical, neurological and nasal examinations will be conducted, adverse events and concurrent medications will be recorded. Participants will bring their device components, study diary and any used and unused study drug vials to the site. Study drug compliance will be assessed. POD components (actuators, vial adapters, canisters and POD tips) will be dispensed.

Participants who were previously taking placebo will cross over to active study drug. All participants will receive the active study drug during the six-month open-label period.

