## 8.0 EARLY TREATMENT/STUDY DISCONTINUATION

The investigators at each site will make every reasonable effort to maximize participant retention. However, if an investigator removes a participant from treatment or study, or if a participant declines further treatment or study participation, an Early Discontinuation Visit will be completed as soon as possible following discontinuation of the study drug and or at time of study discontinuation. The Early Discontinuation Visit will contain the same assessments as the Month 12 visit, to allow collection of the main outcome measures. Depending on when the last LP or MRI was conducted, certain procedures may not be required at the Early Discontinuation Visit. If an in-person visit is not possible, site personnel will complete as much of the Early Discontinuation Visit as possible by telephone. All early treatment discontinuation participants will be strongly encouraged to complete all remaining visits through Month 12 visit.

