5.2 Final Analyses and Reporting

All final planned analyses identified in the research plan and in this SAP will be performed in two phases:

- blinded phase:
After the last participant has completed all assessments scheduled for blinded phase (12 months) of the study and the database for this phase has been cleaned and locked. This analysis will only include visits up to and including 12 months.
- follow-up phase:
After the last participant has completed assessments scheduled for the study (18 months) and the complete database has been cleaned and locked. This analysis will only include visits up to and including 18 months.

Any post-hoc exploratory analyses performed to provide support for planned analyses but not identified in this SAP will be documented and clearly identified as unplanned analysis in the manuscript.

6 Statistical Methods

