7.5 Analysis of Secondary Outcomes

Secondary Aims I

Individuals in the active arm with Impel device will demonstrate slower rate of decline on secondary outcomes including CDR-SB, memory composite (Story Recall and FCSRT), and ADCS-ADL MCI in comparison to the placebo arm. Mixed Model repeated measures (MMRM) models similar to the primary analysis will be used.

Secondary Aims V

To determine whether further improvement occurs after 18 months of treatment.

- The analysis will be the same as the primary analysis with data up to the month 18. The null hypothesis is that the treatment difference between active and placebo with Impel device for the ADAS-Cog12 at month 18 is equal to zero.
- Delayed-start analysis is to compare Δ_2 , the treatment differences between active and placebo at the month 18 (delayed-start period) with Δ_1 that at the end of the placebo-controlled period with noninferiority margin as 50% of Δ_1 [1, 2].

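### Secondary Aim V compares the original arms at Month 18, but treatment discontinuers are asked to attend only to Month 12, and the plan does not say that the original allocation stays concealed after Month 12

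*Protocol*

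**What the plan says.** **The Month 18 comparison.** Under Secondary Aims V, SAP 7.5 repeats the primary model with data to Month 18 and tests whether the "treatment difference between active and placebo with Impel device for the ADAS-Cog12 at month 18 is equal to zero". It adds a delayed-start analysis that compares the Month 18 difference with the Month 12 difference, "with noninferiority margin as 50% of" the latter. Both use the arms as first randomised. By then the treatments are the same (Protocol 7.7): "Participants who were previously taking placebo will cross over to active study drug".

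**Follow-up after stopping treatment.** Protocol 8.0 provides for an Early Discontinuation Visit with the Month 12 assessments and then says: "All early treatment discontinuation participants will be strongly encouraged to complete all remaining visits through Month 12 visit". It requests nothing for Months 15 and 18.

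**Masking.** Protocol 15.4 reads: "For the initial 12-month period, neither participants, study partners, site personnel, most Coordinating Center staff, nor PI will know" which treatment is being taken. The Treatment Blinding Questionnaire (Protocol 9.4) is completed at the end of the blinded phase. SAP 5.2 runs the 12-month analysis as a separate step: "After the last participant has completed all assessments scheduled for blinded phase (12 months) of the study" and that database is locked.

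**The concern.** A delayed-start comparison asks whether those who began insulin early are still ahead once both arms take it. The answer depends on two things: Month 18 scores from the participants who were randomised, and raters and participants who do not act on who started when.

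The plan's explicit provisions for both stop at Month 12. People who stop treatment may follow a different course from those who continue, and they may be unevenly split between arms. If their late scores are not sought, the Month 18 difference can move in either direction, and so can the comparison with the 50% margin. On masking, it does no harm to an arm contrast that everyone knows they now take insulin. Knowing that a particular person had been on placebo could do harm, because that knowledge differs by arm.

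**Working it through.** **1. Provisions side by side**

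| Item | To Month 12 | Months 12 to 18 |
|---|---|---|
| Comparison by original arm (SAP 7.4, 7.5) | primary test | null test and delayed-start comparison |
| Visits asked of treatment discontinuers (Protocol 8.0) | encouraged | neither requested nor barred |
| ADAS-Cog12 in the schedule (Protocol Table 4) | every visit from baseline | Months 15 and 18 |
| Blind (Protocol 15.4) | described | not addressed |
| Blinding questionnaire (Protocol 9.4) | once, at the end of the phase | none |

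**2. What the model does with a discontinuer.** Aim V uses the primary model. SAP 7.4 keeps anyone with a baseline and at least one later ADAS-Cog12 score, so discontinuers stay in. Their missing Month 18 value is handled implicitly, from their own earlier scores and from the Month 12 to 18 course of others in the same arm. Protocol 12.0 states the missing-at-random assumption for its mixed models. The others in the arm are mostly people taking insulin. SAP 6.3 covers missing items within an assessment, and the SAP gives no sensitivity analysis for missing Month 18 visits.

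**3. The plan's own figures.** None is given for Month 18. The 15% to 25% dropout in Protocol 12.1 was used to size a 12-month comparison. It is not the share who stop treatment but would still attend, so it cannot serve as the size of this problem.

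**4. Illustration (all inputs assumed).** Let p_A and p_P be the shares of the active and placebo arms without a Month 18 score. Let k be the number of points by which those people do worse than the model predicts, taken as equal in both arms. Higher ADAS-Cog12 is worse, so each arm's mean worsening is understated by p × k, and the difference is off by

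offset = k × (p_A − p_P).

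| p_A | p_P | k = 1 | k = 2 | k = 3 |
|---|---|---|---|---|
| 0.25 | 0.15 | 0.10 | 0.20 | 0.30 |
| 0.20 | 0.15 | 0.05 | 0.10 | 0.15 |
| 0.20 | 0.20 | 0 | 0 | 0 |

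Greater loss in the active arm flatters insulin. Swapping the two shares reverses the sign.

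**5. Against the margin.** Take a Month 12 difference of 2.0 points (assumed; it is one of the differences in Protocol Table 5). The 50% threshold is then 0.5 × 2.0 = 1.0 point. An offset of 0.1 to 0.3 changes the apparent share retained by 0.1/2.0 = 5 to 0.3/2.0 = 15 percentage points.

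**6. Masking.** No arithmetic applies. The documents give no probability that anyone learns an original assignment and no size for an expectation effect, so no figure can be attached.

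**The case against.** **On follow-up.** Protocol 8.0 does not bar later attendance. The Early Discontinuation Visit includes ADAS-Cog12, and for someone who stops during open label the windows in SAP 7.2 could place it at Month 15 or 18. A reader might infer that discontinuers are dropped from Aim V or missing altogether. That goes too far, because they remain in the model and their scores to Month 12, including any off treatment, inform the estimate. What stands is that their later scores are not requested, so little off-treatment information will exist for Months 12 to 18.

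**On masking.** A reader might infer that the original arms are unblinded at Month 12, or that the 12-month analysis unmasks people still awaiting their Month 18 visit. The documents support neither.
- Everyone moves to the same drug and dose, so the switch does not itself require sites to learn who had placebo.
- Protocol 15.9 controls and documents any breaking of the blind and gives no Month 12 end date.
- SAP 5.2 says when the 12-month analysis is run. It does not send results or allocation to sites, and arm-level results do not reveal an individual's arm.
- ADAS-Cog12 is a psychometric test given by certified staff; study partners do not rate it.

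What stands is silence: no passage commits to concealment through Month 18.

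**On importance.** Protocol 4.4 already calls open-label efficacy analyses exploratory and advises caution because they are unblinded. Aim V is also outside the four ordered hypotheses of SAP 6.2. Both points lower the stakes. However, the caution does not retain discontinuers, and SAP 7.5 does not repeat it while setting a formal null hypothesis and margin.

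**Conclusion.** The point holds for Aim V only. The firmer part is follow-up: a stated rule ends at Month 12 while two comparisons by original arm are made at Month 18, which leaves many discontinuers' Month 18 outcomes to a missing-at-random model. The bias cannot be sized or signed from the documents. The 0.1 to 0.3 point figure depends wholly on the assumed 25% versus 15% loss and a 1 to 3 point shortfall, and it is zero if loss and shortfall are equal across arms.

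The masking part is a gap in wording, not evidence of unmasking, and carries no number. The Month 12 primary test and the gatekeeping sequence are untouched.

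**What to change.** - **Protocol 8.0:** where discontinuers are "strongly encouraged to complete all remaining visits through Month 12 visit", move the end point to the Month 18 visit for outcome assessments, whether or not open-label drug is taken.
- **Protocol 15.4 and SAP 5.2:** state that participant-level original allocation is not released to participants, study partners, site staff or raters until the last Month 18 visit has taken place.

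**Cost:** the first change adds up to two already scheduled visits for each discontinuer who agrees. Some will decline, so the missing-at-random assumption will matter less but will not disappear. The second is a wording change, and the 12-month analysis can go ahead as planned.
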